### 1.3 Secondary Objectives

*Phase I*

- Evaluate pharmacokinetics of both duvelisib and venetoclax in CLL/SLL and RS

*Phase II*

- Evaluate preliminary efficacy, including the best objective response rate (ORR), duration of response (DOR) among patients who have achieved a partial response (PR) or CR, progression free survival (PFS), and overall survival (OS) in patients treated with combined duvelisib and venetoclax
- Determine the rate of minimal residual disease (MRD-negative CR) in the bone marrow at six months, one year and two years, and rate of best MRD-negative CR/CRi in the bone marrow
- Determine the association of FISH abnormalities, *TP53*, *NOTCH1*, or *SF3B1* mutations, and *IGHV* mutational status with ORR and CR rate

*Exploratory Objectives:*

- Use both standard (performed prior to initiation of therapy and following one week of duvelisib monotherapy) and dynamic BH3 profiling to determine whether duvelisib therapy enhances mitochondrial priming and how this correlates with response
- Use BH3 profiling (performed prior to initiation of therapy, following one week of duvelisib monotherapy, and after three and six months of combination therapy) to determine whether BCL-2 dependency predicts response to therapy or risk of tumor lysis syndrome. Alternatively, we will determine whether dependency of anti-apoptotic proteins other than BCL-2 (i.e., MCL-1 and BCL-XL) predicts resistance to therapy
- Use Cytometry by Time of Flight (CyTOF) to identify how duvelisib monotherapy and duvelisib and venetoclax combination therapy impacts immune cell subtypes, in particular the ratio of regulatory to conventional T cells
- Determine change in lymph node size following one week of duvelisib monotherapy
- Determine change in quality of life score using quality of life survey (appendix F) after one week of duvelisib monotherapy

CONFIDENTIAL

This document is confidential. Do not disclose or use except as authorized.

## 2. BACKGROUND:

### 2.1 Chronic Lymphocytic Leukemia

Chronic lymphocytic leukemia (CLL) is the most prevalent adult leukemia in the western world, with approximately 19,000 new cases diagnosed in the United States each year. Although a subset of patients will have an indolent disease course, some patients experience more rapidly progressive disease despite multiple lines of therapy, and few patients are cured. Over the past few decades, a deeper insight into the molecular and genetic underpinnings of CLL have helped to elucidate these differences in outcomes and have paved the way for a pharmacologic revolution, with the development of a variety of highly effective and well-tolerated novel targeted agents. Although this has led to an expansion in therapeutic options for patients unable to tolerate traditional chemoimmunotherapy (CIT) and for patients with relapsed/refractory disease or high-risk biology, complete response (CR) rates remain low and responses are not durable in a large subset of patients on novel agent monotherapy. Novel therapeutic combination strategies are urgently needed to deepen responses and improve outcomes.

Among the novel targeted agents available for patients with relapsed/refractory disease and high-risk biology are Bruton's tyrosine kinase inhibitors, such as ibrutinib. Ibrutinib is an oral, covalent inhibitor of BTK, a key component in B-cell signaling. The first phase Ib-II trial of ibrutinib for patients with relapsed/refractory CLL and symptomatic older patients with treatment naïve CLL demonstrated high response rates and an acceptable safety profile. Patients with relapsed/refractory CLL showed an 86% overall response rate (ORR) and 10% CR rate with a median progression free survival (PFS) of 52 months. While patients with deletion 17p (del(17p)) had high response rates, responses were less durable, with a median PFS of 26 months. The confirmatory phase III trial, RESONATE, also demonstrated an improvement in ORR, PFS, and overall survival (OS) of ibrutinib monotherapy compared to ofatumumab in patients with relapsed CLL, leading to full FDA approval of ibrutinib for this population.

Although patients have demonstrated excellent responses to ibrutinib, the effects are not durable for many patients, especially for those with high-risk features such as del(17p). For patients who relapse after ibrutinib, the survival is poor, with median overall survival ranging from 3 months to 23 months in one study. Other patients are not able to tolerate ibrutinib given associated side effects such as atrial fibrillation and bleeding risk. Novel therapeutic options for these patients are urgently needed.

### 2.2 Richter's Syndrome

Although the course for most CLL patients is at least initially an indolent one, it is estimated that between 1% to 11% CLL patients transform to an aggressive lymphoma. The most common transformation event, known as Richter's syndrome (RS), involves CLL transforming into diffuse large B cell lymphoma (DLBCL).

Overall, the prognosis for patients with RS is poor, though response to therapy depends on

CONFIDENTIAL

This document is confidential. Do not disclose or use except as authorized.

whether the disease is clonally related to the antecedent CLL. Patients with clonally unrelated RS have a median survival estimated at 62 months; however, about 80% of patients have clonally-related Richter's, and the median overall survival for these patients ranges from 8 to 14 months depending on the study.

Based largely on extrapolation of data from *de novo* DLBCL, the approach to RS treatment has historically been to use anthracycline containing chemotherapy, most commonly the rituximab, cyclophosphamide, doxorubicin, vincristine, and prednisone (R-CHOP) regimen. The efficacy of this approach has been evaluated in small phase 2 studies such as the German CLL2G trial, which included 15 patients with RS, and the CR rate was only 7%. Recently, data were published by the CLL group at Ohio State University on the use of a dose adjusted infusional regimen of rituximab, etoposide, cyclophosphamide, doxorubicin, vincristine, and prednisone (da-R-EPOCH) in 46 patients with RS. The CR rate of 20% was modest, and the durability of response was short. As such, novel approaches to treating Richter's Syndrome are urgently needed.

### 2.3 Venetoclax

Venetoclax is an oral, potent, selective inhibitor of BCL-2, a key mediator of the intrinsic pathway of apoptosis. BCL-2 inhibits cell death by binding to pro-death, BCL-2 family proteins that activate apoptosis at the level of the mitochondria. CLL cells express high levels of BCL-2 and are dependent on it for their survival, making BCL-2 an attractive therapeutic target. Preclinical studies have demonstrated that venetoclax selectively binds BCL-2 with subnanomolar affinity ( $K_i < 0.01$  nM) and rapidly induces apoptosis in human CLL cells. Venetoclax also has a lower affinity for other anti-apoptotic BCL-2 family proteins, like BCL-XL and BCL-w (> 4,000-fold and > 2,000- to > 20,000-fold lower affinity than to BCL-2, respectively) and therefore has a different safety profile than prior dual BCL-2/BCL-XL inhibitors, which led to dose-limiting thrombocytopenia due to inhibition of BCL-XL. Venetoclax yields an improved therapeutic index by maintaining efficacy against tumor cells while avoiding dose-limiting thrombocytopenia.

In the first-in-human, phase I trial in CLL, venetoclax was well-tolerated and active at all doses studied. There were a total of 116 patients enrolled in the study, which was divided into a dose escalation cohort (n=56), treated with doses ranging from 150 to 1,200 mg, and a dose expansion cohort (n=60), treated with a dose of 400 mg. The most prominent toxicity observed early in the study was tumor lysis syndrome (TLS). The three initial patients treated with venetoclax (with initial dosing at 100 mg or 200 mg) experienced laboratory TLS after the first dose. Despite further reduction in the starting dose to 50 mg and weekly ramp-up to a target dose for each cohort, two patients experienced clinical TLS, with one patient requiring hemodialysis and one fatality due to presumed cardiac dysrhythmia. The risk of TLS was subsequently mitigated with a reduction of the initial dose to 20 mg, extended ramp-up of dosing with weekly increases to 50 mg, 100 mg, and 200 mg per day to the target dose of 400 mg, as well as close monitoring of and prophylaxis against TLS. With these modifications, only one of sixty patients

CONFIDENTIAL

This document is confidential. Do not disclose or use except as authorized.

in the expansion cohort had laboratory findings of tumor lysis and none had clinical sequelae. Other toxicities associated with venetoclax, such as neutropenia and gastrointestinal adverse events, were manageable.

In the initial phase I trial, the ORR, including both the dose-escalation and expansion cohorts, was 79%, with a 20% CR rate. Overall, 5% of patients achieved minimal residual disease (MRD) negativity by 4-color flow cytometry in the peripheral blood, though analysis was not uniformly available. Of note, response rates among patients with del(17p) were similar to the overall cohort, with a 71% ORR and 16% CR rate. Patients with other high-risk features, including unmutated *IGHV*, refractoriness to fludarabine, and bulky disease similarly had excellent responses to venetoclax.

The follow-up landmark, phase II study included 107 patients with del(17p) CLL. An ORR of 79.4% was achieved, with a CR rate of 10%. In a subset of 45 patients evaluated for MRD in peripheral blood, 18 had no evidence of detectable disease. At the time of the analysis, the median duration of overall response, event free survival, time to progression, PFS and OS had not been reached. The estimated 12-month PFS and OS were 72% and 86.7%, respectively. The results of this study led to accelerated approval of venetoclax by the FDA for relapsed or refractory del(17p) CLL. More recently venetoclax has also been tested in patients who relapsed after or were refractory to ibrutinib or idelalisib, a group recently appreciated to have a particularly poor prognosis. Although the sample size in this study is small, there was a less than 5% CR rate.

Venetoclax has since been studied in combination with rituximab. The initial phase Ib trial demonstrated that this combination was well tolerated, efficacious, and associated with a high degree of MRD negativity. This prompted the phase III MURANO trial, a randomized trial of venetoclax plus rituximab versus BR for patients with relapsed/refractory CLL, which demonstrated a 2-year PFS of 84.9% with venetoclax plus rituximab as compared to 36.3% with BR, leading to FDA approval in 2018 of venetoclax in combination with rituximab in CLL patients after one prior line of therapy, independent of del(17p) status.

While the results of venetoclax monotherapy are promising, CR rates range from only 5-20%, and a large subset of patients did not have durable responses, especially those with complex karyotype and/or del(17p). In the phase I study, 35% of patients progressed with 15 months of initiating therapy. Similarly, a phase II trial of patients who were refractory to or relapsed after ibrutinib therapy, showed a median PFS of 22 months. Based on experience with chemoimmunotherapy, achieving CR with MRD negativity is highly beneficial both in terms of remission duration and OS. The use of combination therapy has the potential to deepen responses for this difficult to treat population and thus improve outcomes for patients for relapsed/refractory or high-risk CLL.

For additional information regarding the pharmacology, metabolism, toxicology, and pharmacokinetics, please refer to the venetoclax package insert.

CONFIDENTIAL

This document is confidential. Do not disclose or use except as authorized.

## 2.4 Duvelisib

Another key target in CLL is phosphatidylinositol-3-kinase (PI3K). PI3K is a heterodimeric lipid kinase composed of both a regulatory and catalytic subunit, that serves as a key component of B-cell receptor (BCR) signaling, which is constitutively activated in CLL. Of the four PI3K isoforms, PI3K- $\delta$  and PI3K- $\gamma$ , are preferentially expressed in normal and malignant cells of hematopoietic lineage and have distinct and complementary roles in leukocyte signaling, differentiation, activation and chemotaxis. Inhibition of the PI3K- $\delta$  isoform with idelalisib, for example, is able to de-adhere CLL from the stroma and increase their susceptibility to apoptosis. Idelalisib has also shown clinical activity in patients with CLL, with an ORR of 72% and a median PFS of 15.8 months, and is FDA-approved in combination with rituximab for relapsed/refractory CLL.

Duvelisib, an oral, reversible and selective small molecule dual inhibitor of PI3K- $\delta$  ( $K_d=23\text{pM}$ ) and PI3K- $\gamma$  ( $K_d=243\text{ pM}$ ), has also emerged as a promising therapy for patients with CLL. Preclinical studies have shown that duvelisib inhibits BCR signaling, reduces chemotaxis, and inhibits cytokine mediated proliferation. PI3K- $\gamma$  inhibition also inhibits the tumor-promoting effects of T-cell and myeloid cells in the microenvironment, providing the potential for enhanced anti-tumor effect as compared to PI3K- $\delta$  inhibition alone.

The initial phase I study for duvelisib monotherapy enrolled patients with a variety of hematologic malignancies, including those with CLL. In 55 patients with CLL, the most common adverse events were cytopenias (neutropenia 31%, thrombocytopenia 11%), febrile neutropenia (15%), and pneumonia (11%). Grade 3 ALT/AST increase occurred in 5% of patients and no grade 4 elevations were seen. There were initial concerns regarding infection risk, thus prompting the addition of mandatory infection prophylaxis. This trial demonstrated a maximum tolerated dose of 75 mg twice per day, though patients with CLL responded to lower doses of 25 mg twice per day, thus this lower dose was chosen for the follow-up phase II trial. Even at 25 mg, there was complete suppression of PI3K- $\delta$  ( $>1C_{90}$ ) and partial inhibition of PI3K- $\gamma$  ( $\geq IC_{50}$ ). Of patients with baseline CT scans, 83% had a  $>50\%$  in adenopathy. The best ORR by IW-CLL criteria for patients with CLL was 55%. Patients with del(17p) had similar response rates.

A follow-up phase II trial, DYNAMO, included patients with follicular lymphoma (FL), small lymphocytic leukemia (SLL) and marginal zone lymphoma (MZL). The ORR in the SLL cohort was 68%. The phase III randomized trial of duvelisib vs. ofatumumab (DUO) was designed to seek regulatory approval for duvelisib. The study is currently being analyzed but top-line data reported an improvement in PFS of duvelisib as compared to ofatumumab in patients with R/R CLL, with rates of 13.3 and 9.9 months, respectively, leading to recent FDA approval in September 2018.

For additional information regarding the pharmacology, metabolism, toxicology, and pharmacokinetics, please refer to the duvelisib investigator brochure.

[figure not shown]

CONFIDENTIAL

This document is confidential. Do not disclose or use except as authorized.

## 2.5 Rationale for Duvelisib and Venetoclax Combination Therapy

As venetoclax and duvelisib target pathways fundamental to CLL biology and have distinct mechanisms of action, they offer promise as a combination therapy for the treatment of patients with CLL and RS. Preclinical data further support this combination, as duvelisib therapy has been shown to upregulate BCL-2 transcript levels and protein expression levels and enhance the ability of venetoclax to induce apoptosis in *ex vivo* human CLL cells. BH3 profiling has also previously shown that inhibition of PI3K enhances the apoptotic threshold of CLL cells and sensitivity to BCL-2 inhibition. As PI3K inhibition results in decreased CLL cell adhesion, it has the potential to decrease the protective effects of stromal cells and increases the CLL cells' susceptibility to apoptosis. Although duvelisib had minimal activity in aggressive non-Hodgkin lymphomas in the phase I study, there may be synergy when used in combination with venetoclax in this population. In DLBCL, it has also been shown that PI3K inhibition is synergistic with venetoclax in subtypes of DLBCL.

**Figure 1.** (A) Treatment with a PI3K inhibitor (PI3K) demonstrates an ability to kill CLL cells even in the presence of stroma. (B) PI3K inhibition increases cytochrome release in response to the Bad peptide, suggesting increased BCL-2 dependency following PI3K inhibition ([name] et al., 2012).

This trial provides the unique opportunity to combine agents with known activity in CLL with the goal of inducing higher rates of MRD-negative CR. Patients who achieve MRD negativity can discontinue therapy after a minimum of one year of treatment with close monitoring of recurrent disease, thus providing the opportunity to avoid the toxicities associated with indefinite treatment and significantly reduce costs. This strategy has already been employed in other studies. For example, in a phase II trial of venetoclax plus rituximab, 13 patients who had responded to therapy discontinued all treatment. Among the 11 patients with MRD-negative CR, all remained progression free off treatment, with some patients off therapy for greater than one year. Numerous ongoing trials in CLL are using MRD status as a decision point to guide treatment duration.

While duvelisib and venetoclax have distinct mechanisms of action, they have potential for significant drug-drug interactions, given their simultaneous effects on CYP3A4. We will therefore initially add venetoclax to duvelisib at a lower dose than used in the initial phase I clinical trials and monitor closely for toxicity.

CONFIDENTIAL

This document is confidential. Do not disclose or use except as authorized.

## 2.6 Rationale for inclusion of Richter's Syndrome patients

In addition to the studies in CLL, venetoclax monotherapy has also been studied in a small number of patients with RS, where 3/7 patients (43%) achieved a partial response, including one patient who remains in remission on treatment now for over 18 months. Venetoclax generally had a favorable toxicity profile in these RS patients that looked similar to its toxicity profile in CLL/SLL. Direct evidence for the efficacy of PI3K-inhibitors such as duvelisib in RS remains anecdotal. However, an interesting line of indirect evidence for the utility of the PI3Ki in RS comes from the large, randomized phase 3 trials of duvelisib and an older PI3Ki idelalisib, where a very low incidence of RS was observed (Flinn et al., *Blood*, 2018 and Furman et al., *NEJM*, 2015). It has been hypothesized that the immune-stimulating properties of PI3K inhibition may enhance anti-tumor immune surveillance, thereby eliminating early Richter's clones that may emerge on treatment. Additional prospective clinical studies of PI3Ki as a component of RS therapy are warranted, and given the known single agent activity of venetoclax in RS and the potential for synergy with duvelisib based on the preclinical data of this combination in CLL, we now plan to explore this combination in a separate exploratory cohort in this trial.

CONFIDENTIAL

This document is confidential. Do not disclose or use except as authorized.

## 2.7 Correlative Studies Background

### BH3 Profiling:

This study will incorporate a laboratory technique known as BH3 profiling, which is a functional assay that uses synthetic peptides that mimic the BH3 domains of pro-apoptotic BCL-2 family members to measure mitochondrial “priming”, or how close a cell is to its apoptotic threshold. This tool is also extremely powerful in that it can identify which anti-apoptotic proteins (i.e., BCL-2, BCL-XL, MCL-1) the cell relies on for survival. To perform a BH3 profile, individual BH3-only peptides are mixed with gently permeabilized living primary CLL cells, formalin-fixed, and then fluorescence activated cell sorting (FACS) is used to determine the amount of mitochondrial depolarization induced by each peptide as measured by cytochrome c release.

We have previously found that in a small, heterogeneously treated cohort of CLL patients, increased priming was associated with improved clinical response. We have also demonstrated that increased priming was associated with depth of clinical response in relapsed/refractory CLL patients on the M12-175 phase I study of venetoclax. Building on these initial studies, we will incorporate BH3 profiling into this trial to determine whether *in vivo* treatment with duvelisib enhances mitochondrial priming and or BCL-2 dependency and whether this correlates with response to combination therapy with venetoclax. We will also use BH3 profiling to determine whether dependency of anti-apoptotic proteins other than BCL-2 (i.e., MCL-1 and BCL-XL) predicts resistance to therapy. In a similar fashion, we will utilize dynamic BH3 profiling to determine whether short incubations of CLL cells with duvelisib *ex vivo*, enhances mitochondrial priming or BCL-2 dependency, and if these results correlate with clinical response.

### Cytometry by Time of Flight (CyTOF):

Mass cytometry or cytometry by time-of-flight (CyTOF) is a technology for multiparameter single cell analysis that uses heavy metal ions as antibody labels, thus overcoming many of the limitations of fluorescence-based flow cytometry. Previous studies have demonstrated that treatment of CLL with PI3K inhibitors alters immune subsets, including the percentage of regulatory T-cells, which is associated with development of toxicity. As duvelisib is known to have effects on tumor-promoting effects of T-cell and myeloid cells in the microenvironment, we aim to characterize these changes and correlate our findings with both response to therapy (ORR) as well as toxicity. We will plan to use a panel of monoclonal antibodies targeting 35 markers, including 26 surface membrane and 9 intracellular markers. The Wilcoxon matched-pairs signed rank test will be used to compare percentages of T cell subsets obtained from CyTOF at various time points.

CONFIDENTIAL

This document is confidential. Do not disclose or use except as authorized.

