#### **Exploratory Objectives:**

- Use both standard (performed prior to initiation of therapy and following one week of duvelisib monotherapy) and dynamic BH3 profiling to determine whether duvelisib therapy enhances mitochondrial priming and how this correlates with response
- Use BH3 profiling (performed prior to initiation of therapy, following one week of duvelisib monotherapy, and after three and six months of combination therapy) to determine whether dependency of anti-apoptotic proteins other than BCL-2 (i.e. MCL-1 and BCL-XL) predicts resistance to therapy
- Use CyTOF to identify how duvelisib monotherapy and duvelisib and venetoclax combination therapy impacts immune cell subtypes, in particular the ratio of regulatory to conventional T cells, and how this correlates with response and toxicity
- Determine change in lymph node size following one week of duvelisib monotherapy
- Determine change in quality of life score using quality of life survey (appendix F) after one week of duvelisib monotherapy

**Study Design:** This is an open-label, multicenter, phase I/II study of duvelisib in combination with venetoclax for patients with relapsed/refractory CLL/SLL or patients with Richter's Syndrome (RS) of any disease status

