#### 7.4 Adverse Event List for Duvelisib:

In the phase I trial of duvelisib for the treatment of relapsed/refractory (R/R) CLL/SLL, all 55 subjects experienced a treatment emergent adverse event (TEAE). The most frequently occurring TEAEs in R/R CLL/SLL subjects were: diarrhea (47.3%); fatigue (38.2%); neutropenia and cough (each 36.4%); anemia and pyrexia (each 32.7%); upper respiratory tract infection (29.1%); AST increased (27.3%); pneumonia, ALT increased, nausea, decreased appetite, neutrophil count decreased, and arthralgia (each 25.5%); and dyspnea (23.6%).

Treatment-emergent serious adverse events (TESAEs) occurred in 36 (65.5%) R/R CLL/SLL subjects. TESAEs occurring in 2 or more subjects with R/R CLL/SLL were: pneumonia and febrile neutropenia (each 16.4%); disease progression and pneumonitis (each 7.3%); fatigue,

CONFIDENTIAL

This document is confidential. Do not disclose or use except as authorized.

colitis, and diarrhea (each 5.5%); and pyrexia, constipation, stomatitis, pneumonia pseudomonas aeruginosa, sepsis, and hypercalcemia (each 3.6%).

As of 19 July 2017, 98 patients with CLL/SLL have enrolled in the IPI-145-12 study, an open-label phase 3 extension study for subjects who experienced disease progression in the phase 3 trial comparing duvelisib to ofatumumab. Of these, 89 subjects have received duvelisib 25 mg BID. For the subjects who have received duvelisib, the median exposure is 31.0 weeks (range 2.0 to 126.7 weeks).

Of 85 of 89 (95.5%) subjects who received duvelisib had a treatment emergent adverse event (TEAE); of these, 70 subjects (78.7%) experienced a TEAE assessed as related to duvelisib. TEAEs that occurred in  $\geq 10\%$  subjects included diarrhea (38.2%); neutropenia (24.7%); pyrexia (22.5%); rash (21.3%); colitis, vomiting, asthenia, pneumonia, and cough (each 11.2%); and nausea and decreased appetite (each 10.1%). TEAEs assessed as related to duvelisib that occurred in  $\geq 10\%$  subjects included diarrhea (32.6%), neutropenia (16.9%), and rash (14.6%).

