## 9.2 Cytometry by Time of Flight (CyTOF):

We will obtain samples prior to therapy, after one week of duvelisib monotherapy (cycle 1, day 8) and after three and six months of combination therapy. We will plan to use a panel of monoclonal antibodies targeting 35 markers, including 26 surface membrane and 9 intracellular markers. The Wilcoxon matched-pairs signed rank test will be used to compare percentages of T-cell subsets, NK cells, and monocytes obtained from CyTOF at various time points. As duvelisib is known alter the tumor-promoting effects of T-cell and myeloid cells in the microenvironment, we aim to characterize these changes and correlate our findings with both response to therapy (ORR), complete response (CR) rate as well as toxicity. In particular we will assess how changes in the ratio of regulatory to conventional T cells correlates with immune-mediated toxicities, as has been observed with other PI3K inhibitors.

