***Exploratory endpoints:***

Associations between the change in mitochondrial priming at baseline as compared to at the time of duvelisib monotherapy and between baseline and combination therapy and ORR will be assessed using Wilcoxon rank test. Associations between change in the percentage of cytochrome c release in response to the Bad, HRK and MS-1 peptides and ORR will be assessed using the Wilcoxon rank test. We will determine whether the percentage of regulatory T-cells, NK cells or monocytes at the start of therapy, after one week of duvelisib monotherapy, and after three months of combination therapy correlates with ORR, CR rate or toxicity using the Wilcoxon rank test.

The average change in lymph node diameter measured on day 1 and day 8 will be measured on physical exam and recorded in the medical record.

CONFIDENTIAL

This document is confidential. Do not disclose or use except as authorized.

We will also measure the change in total score using the quality of life (QoL) questionnaire in appendix F.

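### Section 9.2 asks how change in the regulatory-to-conventional T-cell ratio relates to immune-mediated toxicity, but the only outcome test in Section 13.3 uses subset percentages at single time points

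*Combined protocol and SAP*

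**What the plan says.** The question is stated in four places, with increasing precision.

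- **Section 1.3** asks only how treatment "impacts immune cell subtypes, in particular the ratio of regulatory to conventional T cells". It mentions no outcome.
- **Synopsis, Exploratory Objectives** adds the outcome: "in particular the ratio of regulatory to conventional T cells, and how this correlates with response and toxicity".
- **Section 2.7** says "we aim to characterize these changes and correlate our findings with both response to therapy (ORR) as well as toxicity". This sentence names change, but neither the ratio nor immune-mediated toxicity.
- **Section 9.2** is the most exact: "In particular we will assess how changes in the ratio of regulatory to conventional T cells correlates with immune-mediated toxicities". It also adds CR rate as a response outcome.

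Two analyses are specified. In Sections 2.7 and 9.2 there is a paired comparison over time: "The Wilcoxon matched-pairs signed rank test will be used to compare percentages of T-cell subsets, NK cells, and monocytes". Under Exploratory endpoints in Section 13.3 there is one outcome analysis: "We will determine whether the percentage of regulatory T-cells, NK cells or monocytes at the start of therapy, after one week of duvelisib monotherapy". These percentages, together with those from a three-month combination sample, are related to ORR, CR rate or toxicity by a Wilcoxon rank test. No alpha, power or effect size is given for either, as is usual for an exploratory endpoint.

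**The concern.** The promised analysis and the specified analysis differ in predictor and in outcome. A patient's value on C1D8 is the pre-treatment value plus the change under duvelisib. A test on that value alone cannot say which part is related to toxicity, and the hypothesis in Section 9.2 is about the change. The paired test shows whether a subset moves on average; it does not show whether patients whose ratio moves more are the ones who develop toxicity.

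On the outcome side, Section 13.3 gives no event terms, grade, attribution or time window for toxicity, and Section 9.2 does not define immune-mediated. The predictor and the outcome could therefore both be settled after the data are seen. At stake is whether the CyTOF results can support a statement about the mechanism that the protocol sets out to study.

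**Working it through.** **1. The texts side by side**

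| Element | Question (Synopsis, 2.7, 9.2) | Outcome test (13.3) | Paired test (2.7, 9.2) |
|---|---|---|---|
| Predictor | regulatory-to-conventional ratio (Synopsis, 9.2) | percentage of regulatory T cells, NK cells or monocytes | subset percentages |
| Form | change (2.7, 9.2) | level at each time point | change |
| Toxicity outcome | immune-mediated (9.2) | unqualified | none |
| Response outcome | ORR (2.7); ORR and CR rate (9.2) | ORR and CR rate | none |
| Times | baseline, C1D8, three and six months (9.2) | baseline, one week, three months | various |

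No column on the right combines change, the ratio and an outcome. The BH3 analyses in the same Section 13.3 paragraph do use change as the predictor against ORR, so only the CyTOF sentence omits it.

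**2. Level and change are different tests**

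The documents give no CyTOF variances, so what follows is an illustration with assumed inputs. Let baseline and post-treatment values (on a suitable scale) each have SD 1 and correlation r. Let baseline be unrelated to toxicity, and let the groups differ by 1 SD of the change.

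- SD of change = √(2(1 − r)).
- The raw difference between groups is 1 × √(2(1 − r)), and it appears in full in the post-treatment level.
- Because the level has SD 1, the standardised difference on the level is √(2(1 − r)), against 1 on the change.

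Simulated power, two-sided Wilcoxon rank-sum test at 0.05. The 35 is the CLL/SLL phase II total; the 10 patients with the event are assumed.

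| r | √(2(1 − r)) | Change test | Level test |
|---|---|---|---|
| 0.3 | √1.4 = 1.18 | about 0.70 | about 0.84 |
| 0.5 | √1.0 = 1.00 | about 0.69 | about 0.68 |
| 0.7 | √0.6 = 0.77 | about 0.68 | about 0.47 |
| 0.9 | √0.2 = 0.45 | about 0.70 | about 0.18 |

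With 55 patients (35 CLL/SLL plus 20 RS) and 16 events, the change test has about 0.89. The level test has about 0.90, 0.70 and 0.30 at r = 0.5, 0.7 and 0.9. The baseline level alone is significant about 4 to 5% of the time, as it should be. The two tests break even at r = 0.5, where √(2(1 − r)) = 1.

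**3. If only the baseline differs**

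Assume 35 patients, 30% with toxicity, a 1-SD baseline difference and no difference in change. Take baseline SD as 1 to 3 times the SD of change, with the two independent. The implied correlation with C1D8 is k/√(k² + 1), that is 1/√2 = 0.71 to 3/√10 = 0.95. The C1D8 level test is then significant in about 41 to 66% of trials and the change test in about 5%. The planned baseline test is itself significant in about 68 to 71%, and it accompanies more than 90% of the significant C1D8 results.

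**4. Percentage against ratio**

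If the percentage p were taken of regulatory plus conventional T cells, the ratio would be p/(1 − p), a monotone function of p. A rank test on the level would then give the same p-value for either (confirmed numerically). The documents do not state the denominator, and the identity does not carry over to changes.

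**The case against.** The case for leaving the plan alone has real content.

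- Section 2.7 cites earlier work on the regulatory T-cell percentage and toxicity, so the predictor in Section 13.3 has a basis in the protocol. This stands, and is a reason to keep the level tests. It does not supply the analysis that Section 9.2 announces.
- Section 13.3 does test response, through ORR and CR rate. This stands. A reader might infer that response is left out; what is missing is change against response.
- Section 13.3 also tests the percentage at the start of therapy. As step 3 shows, a pure baseline difference would usually be visible there. A reader might infer that such a difference would pass unnoticed as a duvelisib effect; the planned output does not support that.
- A reader might infer that unqualified toxicity means any adverse event, leaving almost nobody unaffected for comparison. Section 9.2 points to immune-mediated events, so that is not a fair reading. The gap is the missing definition.
- The objective is exploratory, no decision rests on it, and Section 9 lets the investigator omit correlative analyses. The samples are scheduled, so the analysis remains possible. All this limits the importance of the point, but does not make the two sections agree.

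**Conclusion.** The mismatch holds and can be read directly from the text: Section 9.2 promises an analysis of change in the ratio against "immune-mediated" events in substance, and no specified test carries it out. The missing elements are the ratio, the change score and a definition of the toxicity outcome. The six-month sample in Section 9.2 is also absent from the Section 13.3 sentence.

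The size of the consequence is not fixed by the documents. Under the assumptions in step 2, the level test loses little or nothing near a baseline/post-treatment correlation of 0.5, loses heavily near 0.9 (0.18 against about 0.70), and does better than the change test at 0.3. A reader might infer that a true association would mostly be missed; that needs a high correlation, which the documents do not state. The firmer argument is one of interpretation: a level cannot separate the pre-treatment immune state from the treatment effect, and the stated question is about the latter.

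This is a worthwhile correction to an exploratory analysis. The primary result and the trial's decision rules are unaffected.

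**What to change.** In Section 13.3, under Exploratory endpoints:

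1. Add, as the main CyTOF association test, the within-patient change in log(regulatory:conventional T-cell ratio) from baseline to C1D8, and also from baseline to the scheduled three- and six-month combination samples.
2. Compare it by Wilcoxon rank-sum test between patients with and without immune-mediated toxicity, and by ORR and CR status.
3. Before analysis, fix the definition of immune-mediated toxicity: event terms, minimum grade and time window, including how events that precede a given sample are handled.
4. Keep the existing level tests, including baseline and the NK-cell and monocyte percentages, as a separate secondary question, and state the denominator of each percentage.
5. Carry the outcome part of the Synopsis objective into Section 1.3 so that the two agree.

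The cost is wording only. Section 9.2 and the correlative sample schedule already provide the blood samples, so no visit or draw is added. The downside is small: patients without an evaluable paired sample drop out of the change analysis, and their number should be reported.
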